Exclusion Criteria		
 1. Pregnant or lactating females 2. Participation in any clinical study with intake of any investigational drug interfering with the study primary endpoint including: 
 ○ Active infection ○ Psychiatric disorders ○ Known systemic anaphylaxis 3. Any concomitant disease affecting the effect of the therapeutic vaccine or interfering with the study primary endpoint 4. Any immunosuppressive treatment except low dose corticosteroids (equivalent to ≤ 10mg prednisolone/day) 5. Prior or current infection with SARS-CoV-2 tested serologically or by throat/nose swab (PCR) 6. History of Guillain-Barré syndrome 7. Positive serological HIV, hepatitis B or C test. In case of positive HBsAg, volunteer must provide proof of hepatitis B vaccination, otherwise volunteer must be excluded. 8. History of relevant CNS pathology or current relevant CNS pathology (e.g. seizure, paresis, aphasia, cerebrovascular ischemia/haemorrhage, severe brain injuries, dementia, Parkinson's disease, cerebellar disease, organic brain syndrome, psychosis, coordination or movement disorder, excluding febrile seizures as child)

Protocol		
Protocol code and Short Title:	P-pVAC-SARS-CoV-2	Date/Version:08.03.2021/V1.4

	
9. Baseline laboratory with lymphocyte count $\leq 1000/\mu\text{l}$
 
10. Only Part I
 
 ○ Acute or chronic, clinically significant psychiatric, hematologic, pulmonary, cardiovascular, or hepatic or renal functional abnormality as determined by the Investigator based on medical history, physical exam, and/or laboratory screening test

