	
11. All parts of the clinical trial
 
 ○ Diabetes mellitus Typ II requiring drug treatment ○ Chronic lung disease requiring drug treatment ○ Any chronic liver disease or unknown liver abnormalities defined as: 
 • ALT and AST $\leq 2.5 \times \text{ULN}$ • γ-GT $\leq 2.5 \times \text{ULN}$ ○ Chronic renal failure defined as GFR $< 60 \text{ ml/min}/1,73\text{m}^2$ ○ Serious pre-existing cardiovascular disease such as NYHA ≥ 1, coronary heart disease requiring coronary surgery or known pAVK \geq grade 2 ○ Sickle cell anemia ○ Obesity (as defined by age adjusted body mass index) 
12. Hospitalization at study inclusion
 
13. Administration of immunoglobulins and/or any blood products within the 120 days preceding study entry or planned administration during the study period
 
14. History of blood donation within 30 days of enrolment or planned donations within the study period
 
15. Known hypersensitivity to any of the components included in the CoVac-1 vaccine
 
16. Pre-existing auto-immune disease except for Hashimoto thyroiditis and mild (not requiring immunosuppressive treatment) psoriasis

Protocol		
Protocol code and Short Title:	P-pVAC-SARS-CoV-2	Date/Version:08.03.2021/V1.4
Description of the Medical Products	
IMP/Drug product/Peptide vaccine: CoVac-1 applied as one multipeptide cocktails consisting of:
 
 1. SARS-CoV-2 peptides: Six promiscuous HLA-DR-restricted peptides (250 µg each) derived from different proteins of SARS-CoV-2 2. XS15: The lipopeptide XS15 is a water-soluble synthetic Pam₃Cys-derivative. As TLR1/2 ligand it will be included as an adjuvant in the peptide vaccine. 
Peptides are synthesized in the GMP-certified Wirkstoffpeptidlabor at the University of Tuebingen ([name]) and will be formulated at the GMP-Center of the University Hospital Tuebingen. The GMP-certified Wirkstoffpeptidlabor specializes in multipeptide cocktails with variable composition and holds a production permit (Herstellungserlaubnis) for different multipeptide cocktails including the TLR 1/2 ligand XS15.
 
 3. Montanide ISA 51 VG: Prior to application, the peptide cocktail (consisting of 6 SARS-CoV-2-derived peptides and XS15) will be emulsified in a water-oil emulsion 1:1 with Montanide ISA 51 VG to a final volume of 500 µl. 	

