4.1.2. Exclusion Criteria

Subjects presenting with any of the following criteria will not be included in the trial:

1. Pregnant or lactating females.
2. Participation in any clinical study with intake of any investigational drug interfering with the study primary endpoint
3. Any concomitant disease affecting the effect of the therapeutic vaccine or interfering with the study primary endpoint
4. Any immunosuppressive treatment except low dose corticosteroids ($\leq 10\text{mg}$ prednisolone/day)
5. Prior or current infection with SARS-CoV-2 tested serologically or by throat/nose swab (PCR)
6. History of Guillain-Barré Syndrome
7. Positive serological HIV, hepatitis B or C test. In case of positive HBsAg, volunteer must provide prove of hepatitis B vaccination, otherwise volunteer must be excluded.
8. History of relevant CNS pathology or current relevant CNS pathology (e.g. seizure, paresis, aphasia, cerebrovascular ischemia/hemorrhage, severe brain injuries, dementia, Parkinson's disease, cerebellar disease, organic brain syndrome, psychosis, coordination or movement disorder, excluding febrile seizures as child)
9. Baseline laboratory with lymphocyte count $\leq 1000/\mu\text{l}$
10. Only Part I:
 - o Acute or chronic, clinically significant psychiatric, hematologic, pulmonary, cardiovascular, or hepatic or renal functional abnormality as determined by the

Protocol		
Protocol code and Short Title:	P-pVAC-SARS-CoV-2	Date/Version:08.03.2021/V1.4

Investigator based on medical history, physical exam, and/or laboratory screening test

11. All parts of the clinical trial

- Diabetes mellitus Typ II requiring drug treatment
- Chronic lung disease requiring drug treatment
- Any chronic liver disease or unknown liver abnormalities defined as:
 - ALT and AST $\leq 2.5 \times$ ULN
 - γ -GT $\leq 2.5 \times$ ULN
- Chronic renal failure defined as GFR $< 60 \text{ ml/min}/1,73\text{m}^2$
- Serious pre-existing cardiovascular disease such as NYHA $\geq I$, coronary heart disease requiring coronary surgery or known pAVK \geq grade 2
- Sickle cell anemia
- Obesity (as defined by age adjusted body mass index)

12. Hospitalization at study inclusion

13. Administration of immunoglobulins and/or any blood products within 120 days preceding study entry or planned administration during the study period

14. History of blood donation within 30 days of enrolment or planned donations within the study period

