4.1.2. Exclusion Criteria

Subjects presenting with any of the following criteria will not be included in the trial:

1. Pregnant or lactating females.
2. Participation in any clinical study with intake of any investigational drug interfering with the study primary endpoint
3. Any concomitant disease affecting the effect of the therapeutic vaccine or interfering with the study primary endpoint
4. Any immunosuppressive treatment except low dose corticosteroids ($\leq 10\text{mg prednisolone/day}$)
5. Prior or current infection with SARS-CoV-2 tested serologically or by throat/nose swab (PCR)
6. History of Guillain-Barré Syndrome
7. Positive serological HIV, hepatitis B or C test. In case of positive HBsAg, volunteer must provide prove of hepatitis B vaccination, otherwise volunteer must be excluded.
8. History of relevant CNS pathology or current relevant CNS pathology (e.g. seizure, paresis, aphasia, cerebrovascular ischemia/hemorrhage, severe brain injuries, dementia, Parkinson's disease, cerebellar disease, organic brain syndrome, psychosis, coordination or movement disorder, excluding febrile seizures as child)
9. Baseline laboratory with lymphocyte count $\leq 1000/\mu\text{l}$
10. Only Part I:
 - o Acute or chronic, clinically significant psychiatric, hematologic, pulmonary, cardiovascular, or hepatic or renal functional abnormality as determined by the

Investigator based on medical history, physical exam, and/or laboratory screening test

11. All parts of the clinical trial

- Diabetes mellitus Typ II requiring drug treatment
- Chronic lung disease requiring drug treatment
- Any chronic liver disease or unknown liver abnormalities defined as:
 - ALT and AST \leq 2.5 x ULN
 - γ -GT \leq 2.5 x ULN
- Chronic renal failure defined as GFR $<$ 60 ml/min/1,73m²
- Serious pre-existing cardiovascular disease such as NYHA \geq I, coronary heart disease requiring coronary surgery or known pAVK \geq grade 2
- Sickle cell anemia
- Obesity (as defined by age adjusted body mass index)

12. Hospitalization at study inclusion

13. Administration of immunoglobulins and/or any blood products within 120 days preceding study entry or planned administration during the study period

14. History of blood donation within 30 days of enrolment or planned donations within the study period

15. Known hypersensitivity to any of the components included in the CoVac-1 vaccine

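### Exclusion criterion 11 defines an excluding liver abnormality as values at or below 2.5 × ULN, contradicting its own lead-in; Part II has no other ALT, AST or γ-GT limit

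*Supplement*

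**What the plan says.** The current version is V1.4, dated 08.03.2021. Section 4.1.2 is a list in which one match is enough to exclude: "Subjects presenting with any of the following criteria will not be included in the trial". Criterion 11 covers every part ("11. All parts of the clinical trial"). Its liver item opens with "Any chronic liver disease or unknown liver abnormalities defined as" and is followed by two bullets. The first is "ALT and AST $\leq 2.5 \times$ ULN"; the second sets the same limit, in the same direction, for γ-GT. The synopsis repeats both bullets with the same sign.

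The two lists differ on another item. Criterion 2 in section 4.1.2 reads, in full, "Participation in any clinical study with intake of any investigational drug interfering with the study primary endpoint". In the synopsis the same criterion continues with three sub-items that are not about study participation: active infection, psychiatric disorders and "Known systemic anaphylaxis". Section 4.1.2 contains none of these sub-items.

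Under section 6.1.2 the investigator reviews the screening results on an eligibility form and confirms in writing that all criteria are fulfilled.

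**The concern.** An exclusion item should describe the state that keeps a person out. The lead-in announces liver disease or abnormality, but the bullets describe normal or only mildly raised values. The item therefore says the opposite of what it sets out to say, in both places that define eligibility.

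Two things are at stake. First, the criterion cannot be audited: anyone checking the written confirmation against the text must either record volunteers with normal values as ineligible or disregard the wording. Second, the criterion gives no protection against enrolling a person with raised enzymes in a trial whose primary endpoint is safety.

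The mismatch on the three conditions in criterion 2 is a smaller fault of the same kind. Two lists in one protocol define eligibility, and they disagree. One of the conditions, systemic anaphylaxis, bears on a risk that section 5.7.2.1 itself names.

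**Working it through.** No figure in the plan depends on this item, so there is nothing to reproduce. The check applies the rule as printed and then looks for other text that would correct or replace it.

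**1. Is the sign really printed this way?** The same direction stands in the V1.4 synopsis and section 4.1.2, and in both places in V1.3 and in V1.2: six occurrences. A PDF reading error is very unlikely. The V1.4 summary of changes lists only criterion 16 for section 4.1.2, so the sign was not mended.

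**2. What do the neighbouring items do?** Within criterion 11, the renal item (GFR below 60), the heart failure item (NYHA I or higher) and the arterial disease item (grade 2 or higher) all describe the abnormal side. The liver item alone describes the other side.

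**3. Apply the rule literally.** Let A = (ALT ≤ 2.5 and AST ≤ 2.5) and G = (γ-GT ≤ 2.5), in multiples of ULN. The protocol does not say whether the bullets combine as A or G, or as A and G, so both are shown.

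| ALT, AST, γ-GT | A | G | Excluded if A or G | Excluded if A and G |
|---|---|---|---|---|
| 1, 1, 1 | true | true | yes | yes |
| 2.5, 2.5, 2.5 | true | true | yes | yes |
| 3, 3, 3 | false | false | no | no |
| 10, 10, 10 | false | false | no | no |
| 3, 1, 1 | false | true | yes | no |
| 1, 1, 5 | true | false | yes | no |

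The first four rows do not depend on the connector: normal values exclude, and values all above the limit do not. The last two rows do depend on it.

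**4. Would reversing the sign settle the rule?** Not fully. With the direction reversed, the profile 3, 1, 1 meets the ALT/AST bullet only if one raised transaminase is enough. The profile 1, 1, 5 meets only the γ-GT bullet. Whether either volunteer is excluded still depends on how the bullets combine.

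**5. Can the criterion be assessed from the listed tests?** The chemistry panels in footnote 13 to Table 1 and in section 6.4.1 list ALT and AST but not γ-GT.

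**6. What else could stop a volunteer with raised enzymes?**

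| Text | Part I | Part II |
|---|---|---|
| Criterion 3, concomitant disease affecting the vaccine's effect or the primary endpoint | yes | yes |
| Criterion 7, hepatitis B or C serology | yes | yes |
| Criterion 10, clinically significant hepatic abnormality as judged by the investigator | yes | no |
| Inclusion 2.1, free of clinically significant health problems | yes | no |
| Inclusion 2.2, pre-existing conditions allowed | no | yes (permits, does not stop) |
| Any other limit on ALT, AST or γ-GT | none | none |

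**7. Who is affected?** Section 1.1.5 reports Part I as completed with 12 volunteers. That leaves 36 − 12 = 24 in Part II.

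**The case against.** The strongest reply is that nobody would apply the item literally. Its intent is plain from the lead-in and the neighbouring items, and Part I enrolled its 12 volunteers under the same sign. A reader might infer that no healthy volunteer is eligible, or that all 36 are eligibility deviations. The documents do not support that as an outcome: the eligibility form is a separate document that is not shown, and it may already carry the intended direction. This part of the reply stands, and it limits the practical consequence. It does not remove the fault, because a criterion that works only when its wording is ignored cannot be checked.

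A reader might also infer that people with liver disease are freely admitted. That goes too far. Criteria 3 and 7 act in both parts, and criterion 10 and inclusion 2.1 act in Part I. The lead-in can also be read so that the numerical definition attaches only to unknown abnormalities; known chronic liver disease would then still exclude. What is left is the absence of any other enzyme limit in Part II.

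Nor is it shown that laboratory adverse events or relatedness calls would be confounded. Chemistry is measured at screening and at Visit 1. Section 9.1.1 does not count a pre-existing condition as an adverse event unless it changes, and section 6.4.2 restricts when grade 1-2 laboratory findings count. The primary decision rule concerns SAEs associated with the vaccine.

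On the second mismatch, it is tempting to say that section 4.1.2 simply admits volunteers with prior anaphylaxis or psychiatric illness. Criterion 15 excludes known hypersensitivity to vaccine components, criterion 8 names psychosis, and criterion 10 covers significant psychiatric abnormality in Part I. None of these equals the synopsis sub-items, so the disagreement remains, but it is narrower than it first looks.

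**Conclusion.** The point holds as a contradiction in operative eligibility text. In V1.4, criterion 11 says the reverse of its lead-in, in both the synopsis and section 4.1.2. For profiles with all values on one side of 2.5 × ULN, this conclusion does not depend on how the bullets combine.

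The forward-looking gap is the 24 Part II volunteers, for whom no other ALT, AST or γ-GT limit exists. This rests on the text alone and assumes nothing about what the eligibility form says or how staff applied the rule in Part I. No endpoint, sample size, power figure or planned analysis changes.

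Two further gaps belong to the same item: the unstated combination of the bullets, and a defining parameter that is absent from the listed chemistry panels. The disagreement between the synopsis and section 4.1.2 on active infection, psychiatric disorders and systemic anaphylaxis is real, separate and smaller.

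**What to change.** Before further Part II screening:

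- Reconcile the direction of the inequality with the lead-in, in the synopsis, in section 4.1.2 and on the eligibility form. The stated 2.5 × ULN figure stays as it is.
- State whether one raised transaminase is enough or both are needed, and how the ALT/AST bullet combines with the γ-GT bullet.
- Reconcile the criterion with the chemistry panels in footnote 13 to Table 1 and section 6.4.1, which do not list γ-GT.
- Reconcile the synopsis and section 4.1.2 on the three conditions under criterion 2. The sponsor must decide where, and for which parts, they apply. Carrying all three into an all-parts criterion would conflict with criterion 10, which limits psychiatric abnormality to Part I, and would sit uneasily with inclusion 2.2; the overlap with criterion 15 also needs attention.

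The cost is a few lines in the next amendment and a matching check of the eligibility form. If γ-GT is not already measured, it also means one added laboratory parameter at screening or a change to the criterion. The statistical plan needs no change.

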5.1. Peptide Vaccine CoVac-1

The IMP/drug product in this study is CoVac-1. The final peptide vaccine is a water-in-oil emulsion of the peptide cocktail as described in detail below and Montanide ISA 51 VG. All components will be provided by the Wirkstoffpeptidlabor of the Department of Immunology in Tübingen together with a “mixing kit” allowing for the mixture of the components (peptide cocktail, Montanide ISA 51 VG) by the pharmacy of the participating centers.

5.1.1. Peptide cocktail

5.1.1.1. SARS-CoV-2-specific peptides (drug substance)

Each volunteer enrolled in the P-pVAC-SARS-CoV-2 trial will receive 6 promiscuous HLA-DR peptides (250 µg each) derived from different proteins of SARS-CoV-2. Details on drug substance can be found in Table 3.

5.1.1.1.1. TLR1/2 ligand XS15 (drug substance)

The lipopeptide XS15 (50 µg), chemical name N-Palmitoyl-S-[2,3-bis(palmitoyloxy)-(2R)-propyl]- (R)-cysteinyl-GDPKHPKSF, a water-soluble synthetic Pam₃Cys-derivative is a TLR1/2 ligand that will be included as an adjuvant in the peptide cocktail.

Protocol		
Protocol code and Short Title:	P-pVAC-SARS-CoV-2	Date/Version:08.03.2021/V1.4

5.1.2. Montanide ISA 51 VG

Prior to application, the peptide cocktail (consisting of 6 SARS-CoV-2-specific HLA-DR peptides and the TLR1/2 ligand XS15) will be emulsified in a water-oil emulsion 1:1 with Montanide ISA 51 VG. Montanide ISA 51 VG is based on a blend of mannide monooleate surfactant and mineral oil and has been used as an adjuvant in more than 200 human vaccine trials. Montanide ISA 51 VG is rendering stable water-in-oil emulsions when mixed with water-based antigenic media.

Protocol		
Protocol code and Short Title:	P-pVAC-SARS-CoV-2	Date/Version:08.03.2021/V1.4

Table 3: SARS-CoV-2 specific HLA-DR vaccine peptides

sequence	HLA restriction	peptide length	position	protein	protein name	protein class
ASWFTALTQHGKEDL	DR	15	50-64	ORF9	nucleocapsid protein	structural
LLLLDRLNQLESKMS	DR	15	221-235	ORF9	nucleocapsid protein	structural
ITRFQTLLALHRSYL	DR	15	235-249	ORF9	spike protein	structural
LSYYKLGASQRVAGD	DR	15	176-190	ORF5	membrane protein	structural
FYVYSRVKNLNSSRV	DR	15	56-70	ORF4	membrane protein	structural
SKWYIRVGARKSAPL	DR	15	43-57	ORF8	n.a.	non-structural

Protocol		
Protocol code and Short Title:	P-pVAC-SARS-CoV-2	Date/Version:08.03.2021/V1.4

5.2. Manufacturing of the Investigational Medicinal Product

5.2.1. SARS-CoV-2-specific peptides (drug substance)

All SARS-CoV-2 vaccine peptides are manufactured by the Wirkstoffpeptidlabor, University of Tübingen, [name], 72076 Tübingen, Germany. The Wirkstoffpeptidlabor holds certificates for the production of GMP grade synthetic peptides and for the formulation of multi-peptide vaccine cocktails including the TLR1/2 ligand XS15. All peptides are synthetic peptides manufactured by well-established solid phase peptide synthesis (SPPS) procedures using Fmoc chemistry.

5.2.2. XS15 (drug substance)

XS15 is delivered as bulkware in GMP-quality from the external manufacturer Bachem AG, [name], CH-4416 Bubendorf in active ingredient quality.

Bachem's manufacturing process is described in a separate "Documentation on XS15 Hydrochloride" of 31.05.2018 by the company. The Wirkstoffpeptidlabor performs a second lyophilization as additional manufacturing step. This manufacturing step is divided into four sub-steps: Reconstitution, combining, aliquoting and lyophilization.

5.2.3. Montanide ISA 51 VG

Montanide is manufactured by Seppic and by the rewarding manufacturer Elaiapharm, respectively.

5.2.4. Peptide cocktail CoVac-1 (drug product)

The peptide cocktail is manufactured by the Wirkstoffpeptidlabor by aseptic filling at the GMP-Center of the University Hospital Tuebingen. Each peptide is solubilized in DMSO and sterile filtered, the obtained peptide solutions are pooled. Water is added and the obtained solution is sterile filtered and filled into single dose vials.

5.3. Labeling of the Investigational Medicinal Product

5.3.1. Peptide cocktail

Peptide cocktails (including the TLR1/2 ligand XS15) will be packaged into sterile containers labeled with an identification code definitely assignable to the P-pVAC-SARS-CoV-2 study and a vial number that will be assigned to the individual study volunteer. The trial medication will be labeled according to § 5 of GCP-V. Samples of the labels are filed in the trial master file (TMF).

The peptide vaccine cocktail will be packaged together with Montanide ISA 51 VG and the mixing equipment into the “mixing kit” and shipped from the *Wirkstoffpeptidlabor* of the Department of Immunology, Tübingen to the pharmacy of the participating center. Shipment will be documented according to standard operation procedures (SOP). The “mixing kit” will be shipped using isolated packaging with an automated temperature control system, whose logging data have to be returned to the *Wirkstoffpeptidlabor* of the Department of Immunology together with the acknowledgement of receipt after delivery of the consignment. The device will be read out to document the correct storage temperatures during shipment. Data will be documented according to SOP. The shipment will be performed by an associate of the *Wirkstoffpeptidlabor* of the Department of Immunology, Tübingen.

5.3.2. Montanide ISA 51 VG

Montanide ISA 51 VG is packed by Seppic and Elaiapharm. Montanide will be packaged together with the peptide cocktail and the mixing equipment into the “mixing kit” and shipped from the *Wirkstoffpeptidlabor* of the Department of Immunology, Tübingen to the pharmacy of the participating center, as described above.

5.4. Storage of the Investigational Medicinal Product

Trial medication will be stored at the pharmacy of the participating center and must be kept in a locked area with access restricted to designated trial staff. The “mixing kit” including the peptide cocktail and Montanide ISA 51 VG must be stored in accordance with manufacturer’s instructions at -20°C and dry. The investigator must ensure that the investigational products are stored according to the sponsor’s instructions (temperature, light and humidity) and should control the integrity of the packaging upon receipt. If concerns about the quality or appearance of the investigational products arise, the products may not be dispensed. In this case, the principal investigator must be contacted immediately.

